4.1 Objectives

Primary objective

To confirm the superiority of liraglutide at the maximum tolerated dose (0.6 mg, 1.2 mg or 1.8 mg) versus placebo when added to metformin with or without basal insulin treatment in controlling glycaemia in children and adolescents (ages 10–17 years) with type 2 diabetes.

Secondary objectives

To assess and compare the effect of liraglutide versus placebo in combination with metformin with or without basal insulin treatment on:

- Parameters of glycaemic control
- Parameters of beta-cell function
- Parameters of body composition
- Vital signs
- Growth velocity (if subject is still growing)
- Safety and tolerability
- Growth and pubertal development at 1 and 2 year follow up after trial drug cessation at week 52

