1.1 Trial information

Trial design

This is a multi-centre, 26-week randomised double-blind, parallel-group, placebo-controlled clinical trial followed by a 26-week open-label extension in subject' aged 10-17 years with type 2 diabetes. After being titrated to 2000 mg of metformin or maximum tolerated dose (MTD) (metformin dose must be ≥ 1000 mg and ≤ 2000 mg) subjects will be randomised 1:1 to receive liraglutide (1.8 mg or MTD) or liraglutide placebo. Subjects treated with basal insulin will continue treatment with basal insulin.

Subjects already treated with 2000 mg or more of metformin and with a stable dose for at least 56 days prior to Visit 1 may advance directly to randomisation (Visit 7) when eligibility according to the inclusion and exclusion criteria has been confirmed. Subjects who are treated with basal insulin should in addition to the stable dose of metformin have a stable dose of basal insulin for at least 56 days in order to advance directly to Visit 7.

After 26 weeks of blinded treatment, the treatment allocation will be unblinded. Subjects treated with liraglutide will continue their trial medication until end of treatment. Subjects treated with liraglutide placebo will discontinue their liraglutide placebo treatment. Rescue treatment will be allowed for subjects in both treatment groups experiencing confirmed hyperglycaemia. Subjects on rescue medication will stay in the trial.

Subjects treated with liraglutide for more than 3 months will complete 1 and 2 year follow-up visits.

[figure not shown]

Figure 1 Overview of Trial Design

Liraglutide
Trial ID: NN2211-3659
Statistical Analysis Plan
EurdraCT No.: 2011-002605-29

Date: 25 June 2018 Vovo Nordisk
Version: 2.0
Status: Final
Page: 6 of 25

Primary objective

To confirm the superiority of liraglutide at the maximum tolerated dose (0.6 mg, 1.2 mg or 1.8 mg) versus placebo when added to metformin with or without basal insulin in controlling glycaemia in children and adolescent (ages 10–17 years) with type 2 diabetes.

Secondary objectives

To assess and compare the effect of liraglutide versus placebo in combination with metformin with or without basal insulin treatment on:

- Parameters of glycaemic control
- Parameters of beta-cell function
- Parameters of body composition
- Vital signs
- Growth velocity (if subject is still growing)
- Safety and tolerability

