3.2 Handling of missing data

If an assessment has been made both at screening and randomisation, and if not otherwise specified, the value from the randomisation visit will be used as the baseline value. If the value measured at the randomisation visit is missing and the assessment also has been made at screening, then the screening value will be used as the baseline value.

For efficacy variables missing values will be imputed as described in protocol section 17.3 and 17.4 (section 3.5 and 3.6 in this SAP).

Data collected after treatment discontinuation or initiation of rescue treatment (see protocol section 5.3.5) will be considered missing in some of the efficacy analyses as described in protocol section 17.3 and 17.4 (section 3.5 and 3.6 in this SAP). Data collected after treatment discontinuation will be data from withdrawals collected at either Visit 17 or Visit 25 (see protocol section 8.1.7) in case the measurement is within the visit window (\pm 5 days) of a planned visit.

For safety variables missing values will not be imputed, except for 'pulse' which will be imputed as described for the secondary efficacy endpoints (section 3.6).

For subjects who received rescue medication, all data collected after initiation of rescue medication will be included.

Laboratory values below the lower limit of quantification (LLOQ) will be set to ½LLOQ.

Liraglutide
Trial ID: NN2211-3659
Statistical Analysis Plan

Date: 25 June 2018 Version: 2.0
Status: Final

Page:

13 of 25

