3.3 General considerations

EurdraCT No.: 2011-002605-29

Novo Nordisk will be responsible for the statistical analysis and reporting. Analysis and reporting will be based on pooled data from all sites.

The statistical analyses will be performed with a significance level of 5% (two-sided tests).

For all endpoints analysed statistically, estimated mean treatment differences will be presented together with two-sided 95% confidence intervals and p-values.

The fixed effects in the models described in the following sections are defined as:

- 'age group' is '10-14' and '>14 years' at end of trial, where age at end of trial is calculated as age at baseline + 1 year.
- 'concomitant diabetes treatment at baseline' is determined by the prescribed insulin dose at baseline. The fixed effect will be 'Y' for all subjects with a prescribed insulin dose above zero at baseline, and 'N' otherwise.
- 'region' is defined as 'Asia', 'Europe', 'North America', 'South America' and 'Rest of the world'. A list of the countries in each region can be found in the NN2211 project statistical programming specification (4).

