3.6.3 Safety endpoints

All safety endpoints will be presented using the safety analysis set. Unless otherwise specified safety endpoints will be presented only by descriptive statistics.

Change from baseline at 26 and 52 weeks of treatment unless otherwise stated

- Clinical evaluations (physical examination including fundoscopy [fundoscopy at 26 and 52 weeks])
- ECG with rhythm strip (at 26 and 52 weeks)
- Laboratory tests:
 - Haematology (haemoglobin, haematocrit, thrombocytes, erythrocytes, leucocytes and differential count (eosinophils, neutrophils, basophils, lymphocytes and monocytes)
 Biochemistry (creatinine, creatine kinase, urea, albumin, bilirubin (total), ALAT, ASAT, sodium, potassium, alkaline phosphatase, calcium, calcium (albumin corrected), amylase and lipase)
 - Hormones (calcitonin, prolactin, FSH, estradiol, LH, testosterone, DHEAS, CEA and TSH, IGF-1, IGFBP-3
 - First morning urinalysis (Micro albumin, creatinine, albumin:creatinine ratio calculated, protein, ketone, glucose, pH)
 - o Biochemical parameters of bone metabolism: Alkaline Phosphatase, NTX, CPX, P1NP
 - o Formation of anti-liraglutide antibodies (at 26 and 53 weeks)
- Pulse
- Pubertal assessment/ progression (Tanner staging), DHEAS, LH, FSH, estradiol in females and testosterone in males
- Height SDS versus baseline at 26 and 52 weeks
- Bone age assessment (x-ray of left hand and wrist) at 52 weeks

In addition the following will be assessed at 26, and 52 weeks:

 Assessment of compliance (questioning of subjects and subjects legally acceptable representative)

Liraglutide		Date:	25 June 2018	Novo Nordisk
Trial ID: NN2211-3659	CONFIDENTIAL	Version:	2.0	
Statistical Analysis Plan		Status:	Final	
EurdraCT No.: 2011-002605-29		Page:	20 of 25	

• Growth (height) velocity in cm/year and height (growth) velocity SDS (if subject is still growing). A growth (height) velocity < 1.0 cm/year is defined as no longer growing.

Collected throughout the trial:

- Hypoglycaemic episodes (see details below)
- AEs and serious adverse events (SAEs) (see details below)

Pulse

Pulse will be analysed with a similar method as for the primary analysis for the primary endpoint (as described for the secondary confirmatory and supportive efficacy endpoints).

Height SDS

Height SDS will be calculated using the same formula as described for BMI SDS (see section 3.6.1) The values for M, S and L are downloaded from

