4.2 Handling of missing data

For safety variables it was stated in the protocol that missing values (including intermittent missing values) would be imputed using the last observation carried forward (LOCF) on post-baseline measurements. The analyses on safety parameters will be performed using a pattern mixture model with multiple imputation and missing values will therefore not be imputed using the LOCF method.

4.3 **Definition of fixed effects**

The fixed effect 'region' was not specified in the protocol, but in a sensitivity analysis the regions were described as: North America, Asia including Russia, Europe including Israel, South America including Mexico. To align with other NN2211 trials, the regions are defined as has been done overall for the NN2211 project. The only difference from the description in the protocol is that Russia is not assigned to region Asia, but is assigned to region Europe.

The fixed effect 'concomitant diabetes treatment at baseline' was described as 'diet and exercise alone vs. diet and exercise plus metformin and/or basal insulin'. As all subjects were to take metformin at baseline the definition is updated to with/without basal insulin at baseline (see section 3.3)

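### Growth velocity is named for comparison with placebo, but no adjusted between-arm difference or confidence interval is prespecified for height or growth velocity

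*SAP*

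**What the plan says.** The secondary objectives in protocol 4.1 and SAP 1.1 open with "To assess and compare the effect of liraglutide versus placebo in combination with metformin with or without basal insulin treatment on", and the list beneath includes "Growth velocity (if subject is still growing" with the bracket then closed.

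SAP 3.6.3 puts height SDS, growth velocity and height velocity SDS among the safety endpoints, under the rule "Unless otherwise specified safety endpoints will be presented only by descriptive statistics". The one stated exception is "Pulse will be analysed with a similar method as for the primary analysis for the primary endpoint". Protocol 17.4.3 has the same default and the same exception. SAP 3.6.3 goes on to define how the three growth measures are calculated, but gives no contrast between arms.

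SAP 3.3 ties effect estimates to modelling: "For all endpoints analysed statistically, estimated mean treatment differences will be presented together with two-sided 95% confidence intervals and p-values".

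Two SAP statements on safety variables disagree. Section 3.2: "For safety variables missing values will not be imputed, except for 'pulse". Section 4.2: "The analyses on safety parameters will be performed using a pattern mixture model with multiple imputation".

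A subject with velocity below 1.0 cm/year counts as no longer growing (protocol 4.2, SAP 3.6.3). The visits one and two years after treatment are only for subjects who had more than 3 months of liraglutide.

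**The concern.** A comparative objective needs a planned comparison. Under SAP 3.3 a treatment difference with an interval comes only with a statistical analysis, and SAP 3.6.3 gives the growth measures none.

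Growth is not a minor outcome here. Protocol 3.1.5 and section 18 assume that the benefit and risk seen in adults carry over to children, and name growth and pubertal development as the exception. Yet waist circumference and blood pressure receive a pattern mixture model and an MMRM (SAP 3.6.2), while height receives neither. No placebo comparison can be recovered at the 1- and 2-year visits, because placebo subjects do not attend them.

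The velocity summary has a further weakness. Whether a subject is still growing is decided by velocity, which is the outcome itself. If the tables follow that condition, as the wording suggests, a child whose velocity falls below 1.0 cm/year leaves the summary. Should liraglutide slow growth, this would remove the most affected subjects from that arm and pull the comparison towards no difference.

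**Working it through.** **Is a contrast planned anywhere?**

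- Objective: comparative, and growth velocity is named (protocol 4.1, SAP 1.1).
- Default for safety endpoints: descriptive (protocol 17.4.3, SAP 3.6.3).
- Exception: pulse only.
- Difference with 95% CI: only where an endpoint is analysed statistically (SAP 3.3).
- SAP 4.2: could be read as promising a model for all safety parameters. SAP 3.2 limits imputation to pulse and 3.6.3 limits modelling to pulse, so 4.2 cannot be relied on for growth.

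No contrast for height or velocity follows from these sections.

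**The plan's own sample size.** Protocol 17.1 sizes the trial on HbA1c alone. The diluted effect is 0.9 × (1 − 0.22) = 0.702, with SD 1.2, two-sided 5% and 80% power. A noncentral-t calculation gives 47 per arm (power 80.1%), so 94 in total, as stated. The documents give no precision for any growth outcome, so there is nothing further to reproduce.

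**What precision could an interval have?** Half-width = t(0.975, n1+n2−2) × SD × √(1/n1 + 1/n2), unadjusted. Protocol 6.1 expects 63 completers, about 31 per arm. The SDs and the share still growing are my assumptions, because the documents give neither.

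Change in height SDS, 31 per arm: √(2/31) = 0.254 and t(60 df) = 2.00.

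- SD 0.2: 2.00 × 0.2 × 0.254 = 0.10 SDS
- SD 0.3: 2.00 × 0.3 × 0.254 = 0.15 SDS

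Velocity, 63 subjects split evenly. The half-width in SD units is converted to cm/year for three assumed SDs:

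| Share of the 63 contributing | Half-width (SD units) | SD 1 | SD 2 | SD 3 |
|---|---|---|---|---|
| 100% | 0.50 | 0.50 | 1.01 | 1.51 |
| 75% | 0.59 | 0.59 | 1.17 | 1.76 |
| 50% | 0.73 | 0.73 | 1.46 | 2.18 |
| 25% | 1.08 | 1.08 | 2.17 | 3.25 |

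For the 50% row there are 15.75 per arm: √(2/15.75) = 0.356, t(29.5 df) = 2.044, product 0.73. An uneven split hardly matters: 37 and 26 subjects give 0.51 SD, against 0.50. The lower rows are relevant because protocol 6.3 lets up to 70% of randomised subjects be above 14, using the protocol's definition of age at end of treatment.

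**The case against.** The strongest reply is that the trial was powered for HbA1c, the protocol itself made safety endpoints descriptive, and the SAP has not departed from it. All of that is true. Limited power is a good reason not to test growth. It does not justify omitting the estimate, since the interval shows what the trial can and cannot exclude.

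A second reply is that n, mean and SD by arm would let any reader form an unadjusted difference and interval. That also stands, if those summaries are shown by arm. What is missing is a prespecified estimate adjusted for baseline and strata. It would be wrong to say that no difference could ever be derived.

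A third reply is that height SDS and height velocity SDS are already standardised for age and sex through their reference values. This is correct, so a charge that the growth scores ignore age and sex would fail. Standardising scores still does not supply a treatment contrast.

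Some stronger readings are tempting but unsupported:

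- **Arms combined.** A reader might infer that growth data are pooled over treatment. The pooling stated in SAP 3.3 is over sites: "Analysis and reporting will be based on pooled data from all sites".
- **Hormones merged over sex and pubertal stage.** SAP 3.6.3 specifies no layout for LH, FSH, DHEAS or IGF-1. Silence is not an instruction to combine.
- **An on-treatment comparative objective for puberty.** Pubertal development is named as an objective only for the later follow-up. The comparative growth objective on treatment is growth velocity.

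**Conclusion.** The point holds in a limited form. A named comparative objective has no prespecified, adjusted between-arm estimate with a 95% CI, and the 52-week period is the only time when randomised groups can be compared on growth. The outcome-based definition of still growing adds a risk of bias if it restricts the velocity summary. The SAP also contradicts itself on whether safety parameters other than pulse are modelled.

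The primary analysis and the test hierarchy are unaffected. The interval now missing would be about ±0.10 to 0.15 SDS for change in height SDS (assumed SD 0.2 to 0.3, 31 per arm). For velocity with an assumed SD of 2 cm/year it would be about ±1.0 cm/year if all 63 completers contribute and about ±1.5 if half do. All are unadjusted. Adjustment may narrow them, but the documents do not show by how much. This should be corrected.

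**What to change.** In SAP 3.6.3 add an estimation-only ANCOVA on observed data, outside the test hierarchy. Effects are treatment, stratification groups (gender by age group) and baseline height SDS. Report the liraglutide minus placebo difference with its 95% CI for:

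- **Change in height SDS** at weeks 26 and 52, in all subjects with a height measurement.
- **Height velocity** at week 52, either in all subjects with a measurement or in a growing subset fixed at baseline, for example epiphyses not fused on the Visit 7 x-ray. On-treatment velocity should not define the subset.

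Week 52 suits velocity because SAP 3.6.3 already limits the week-26 velocity SDS to spotting outliers. SAP 3.3 would attach a p-value by default, so say that the interval is for estimation and that no confirmatory claim will rest on it.

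Rewrite SAP 4.2 to agree with SAP 3.2 and 3.6.3: either name pulse (and whatever else is intended) as modelled, or extend the other two sections. Presenting LH, FSH, DHEAS and IGF-1 by sex is an optional layout request.

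The heights and x-rays are already collected, so the cost is a few extra tables. The intervals will be wide and should be reported as such. The change belongs in the SAP before database lock; if added later, it should be labelled post hoc.

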3.7 Exploratory analyses

To evaluate the influence of intake of insulin on the treatment effect on change in HbA_{1c} at week 26 and 52 a repeated measurement analysis (MMRM) model including treatment interaction with insulin at baseline will be performed. All data points for all visits, but excluding data collected after treatment discontinuation or initiation of rescue medication, will be used. Fixed effects in the model are treatment, stratification groups (gender*age group), diabetes medication at baseline and treatment by diabetes medication at baseline interaction. The baseline HbA_{1c} will be included as a covariate. All factors and covariates will be nested within visit. If possible, an unstructured covariance matrix will be used.

3.8 Interim analysis

NA

3.9 Sequential safety analysis/safety monitoring

An external data monitoring committee (DMC) was established to independently review and evaluate accumulated unblinded safety data from the trial in order to protect the safety of the subjects and to evaluate the evolving risk-benefit if required. See protocol for details.

Novo Nordisk constituted an internal safety committee to perform ongoing safety surveillance. The safety committee conducted ongoing monitoring of blinded safety data. The safety committee could recommend unblinding of any data for further analysis, and in this case an independent ad hoc group would be established in order to maintain the blinding of the trial personnel.

3.10 Explorative statistical analysis for pharmacogenetics and biomarkers

NA

3.11 PK data

The liraglutide concentrations will be listed.

Liraglutide Trial ID: NN2211-3659 Statistical Analysis Plan EurdraCT No.: 2011-002605-29

CONFIDENTIAL

Date: Version: Status: Page:

25 June 2018 | Novo Nordisk 2.0 Final 23 of 25

Changes to the statistical analyses planned in the protocol 4

This statistical analysis plan follows the protocol with the following clarifications:

4.1 Sensitivity analysis for the primary endpoint on all randomised subjects

The primary analysis is based on FAS which includes all randomised subjects receiving at least one dose of liraglutide/liraglutide placebo. Due to an FDA request to change in the primary analysis, the primary estimand is the "treatment policy" estimand, and therefore it is appropriate to add a sensitivity analysis of the primary endpoint including all randomised subjects.

4.2 Handling of missing data

For safety variables it was stated in the protocol that missing values (including intermittent missing values) would be imputed using the last observation carried forward (LOCF) on post-baseline measurements. The analyses on safety parameters will be performed using a pattern mixture model with multiple imputation and missing values will therefore not be imputed using the LOCF method.

4.3 **Definition of fixed effects**

The fixed effect 'region' was not specified in the protocol, but in a sensitivity analysis the regions were described as: North America, Asia including Russia, Europe including Israel, South America including Mexico. To align with other NN2211 trials, the regions are defined as has been done overall for the NN2211 project. The only difference from the description in the protocol is that Russia is not assigned to region Asia, but is assigned to region Europe.

The fixed effect 'concomitant diabetes treatment at baseline' was described as 'diet and exercise alone vs. diet and exercise plus metformin and/or basal insulin'. As all subjects were to take metformin at baseline the definition is updated to with/without basal insulin at baseline (see section 3.3)

4.4 Supportive secondary endpoints

The mean post prandial increment is added as an endpoint, as this endpoint has been presented in other trials in project NN2211. The mean post-prandial increment will be analysed as the other supportive secondary endpoints. The post prandial increments after breakfast, lunch and dinner will only be presented by descriptive statistics, whereas in the protocol they were planned to be analysed.

The BMI percentile will also only be summarised, as it is closely related to the BMI SDS.

Liraglutide
Trial ID: NN2211-3659
Statistical Analysis Plan

Date: 25 June 2018 Version: 2.0
Status: Final

Page:

24 of 25

4.5 Statistical analyses of the confirmatory and supportive secondary endpoints

In the protocol it is stated the confirmatory and supportive secondary endpoints 'will be analysed with the same method as the primary efficacy endpoint'. It has been clarified that the endpoints analysed with the same method as the primary efficacy endpoint will be analysed using the primary analysis for the primary endpoint (the pattern mixture model) and, in addition, using the MMRM sensitivity analysis described as no. 4 for the primary analysis (see section 3.5). These analyses have been described in detail in sections 3.6.1 and 3.6.2.

4.6 Exploratory analyses

EurdraCT No.: 2011-002605-29

To evaluate the influence of intake of insulin on the treatment effect on change in HbA1c at week 26 and 52 an exploratory analysis including treatment and diabetes medication at baseline interaction has been added.

